2.3.1. Description of Randomization and Study Arms

Randomization will be conducted at the level of the cluster (1 cluster = 1 health facility). We will randomize 15 clusters evenly to one of three arms: (1) standard of care; (2) optimized standard of care (optimized with support for delivery of standard of care services including support for staff training, job aids, and quality of service delivery); or (3) group HIV self-testing. All patients enrolled at the site will follow the HIV testing assignment for the cluster in which they are randomized. We will use block randomization, blocking on variables that might predict outcomes, including facility type (hospital/health center), location (rural/urban), region (central or southern), and whether facilities have separate or combined STI and OPD clinics. This will help minimize residual confounding that can result in cluster randomized trials. We will then randomly allocate one cluster from each block to each of the three study arms. Clusters will be randomized to achieve a 1:1:1 allocation to each study arm.

Description of Study Arms

Microsoft Excel will be used to randomly assign clusters. Clusters will be assigned to one of three arms:

1. Standard of care arm: Facilities randomized to the standard of care arm will continue with standard of care without any intervention from the study team. Provider-initiated-testing-and-counseling (PITC) is standard of care for both OPD and STI clients. OPD or STI providers tell patients about HIV testing and refer them to the standard HIV testing services room at the health facility. HIV testing activities completed under standard of care will vary by facility based on adherence to national guidelines for PITC.

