2.5. STATISTICAL METHODS

2.5.1. Outcome Measures

Power Calculations and Statistical Analysis for Primary Outcome Measures

We have 15 clusters available for randomization, and therefore, estimated our sample size assuming a fixed number of clusters (k) and an equal number of clusters per arm (k=5). We also assumed an equal number of participants per cluster (n=1,000) for a total sample size of 5,000 participant per arm (15,000 total). Assuming a type I error of 0.05, an intra-cluster correlation of 0.004, we would expect at least 95% power to detect study arm testing coverage of 5% in study arm 1, at least 10% in study arm 2, and 60% in study arm 3.

We will calculate descriptive statistics, including mean/median, variation (standard deviation, kurtosis), range, and frequency distributions for the demographic and clinical characteristics, overall and by study arm. The outcomes of interest include the proportion of participants tested and HIV-positivity among those tested. Differences in the prevalence of each of the outcomes of interest will be examined by study arm as well as by other factors of interest including demographic characteristics (e.g., age, gender), clinical characteristics (e.g., reason for clinic visit), and structural factors (e.g., geographic location). The differences will be evaluated using t-tests, Mann-Whitney U test (or other non-parametric tests), chi-square methods, and Fisher's exact test as appropriate. In order to assess factors associated with HIV testing/positivity, we will use hierarchical linear models in order to account for clustering of effects within each clinic. Separate models will be developed for each outcome of interest and covariates of interest include patient characteristics (e.g., age, gender) and other structural and contextual factors.

Qualitative Analysis for Secondary Outcome Measures

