5. STATISTICAL METHODS

5.1. Outcome Measures

3.5.1.1 Sample Size and Statistical Analysis for Primary Outcome Measures

We will have 15 clusters (facilities) available for randomization, and therefore, estimated our sample size assuming a fixed number of clusters (k) and an equal number of clusters per arm. We also assumed an equal number of participants per cluster. The below calculations were determined using a minimum sample size. Assuming a type I error of 0.05, an intracluster correlation of 0.004 and sample sizes of 600 HIV-positive patients per arm, we have 89% power to detect a difference in testing coverage of 20% in study arm 2 (optimized standard of care) and 40% in study arm 3 (self-testing). Because we are uncertain about the proportion of partners who will test under each arm, we have considered a range of possibilities, with the majority of scenarios providing at least 87% power to detect a difference between the two arms of interest (optimized standard of care and self-testing) (Figure 4).

We will calculate descriptive statistics, including mean/median, variation (standard deviation, kurtosis), range, and frequency distributions for the demographic and clinical characteristics, overall and by study arm. The outcomes of interest include the proportion of partners tested and HIV-positivity of partners. Differences in the prevalence of each of the outcomes of interest will be examined by study arm as well as by other factors of interest including demographic characteristics (e.g., age, gender), clinical characteristics (e.g., reason for clinic visit), and structural factors (e.g., geographic location). The differences will be evaluated using t-tests, Mann-Whitney U test (or other non-parametric tests), chi-square methods, and Fisher's exact test as appropriate. In order to assess factors associated with partner's HIV testing/positivity, we will use hierarchical linear models in order to account for clustering of effects within each clinic. Separate models will be developed for each outcome of interest and covariates of interest include patient characteristics (e.g., age, gender) and other structural and contextual factors.

Qualitative Analysis for Secondary Outcome Measures

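### In both aims, the tests named for differences between arms carry no cluster adjustment although facilities are randomized, and no analysis is designated as the primary test of self-testing against optimized standard of care.

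*Combined protocol and SAP*

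**What the plan says.** Section 2.3.1 randomizes whole health facilities in blocks: "We will then randomly allocate one cluster from each block to each of the three study arms". Section 3.3.1 carries the same allocation into Aim 2. The primary comparison in each aim is self-testing against optimized standard of care (sections 2.1.1 and 3.1.1).

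Both power statements allow for clustering. Section 2.5.1 uses five clusters of 1,000 per arm and an ICC of 0.004. Section 3.5.1.1 uses "an intracluster correlation of 0.004 and sample sizes of 600 HIV-positive patients per arm".

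For the analysis, section 2.5.1 says "Differences in the prevalence of each of the outcomes of interest will be examined by study arm", along with other factors. It gives the method for these comparisons as follows: "evaluated using t-tests, Mann-Whitney U test (or other non-parametric tests), chi-square methods, and Fisher's exact test as appropriate". Section 3.5.1.1 repeats this for partners: "The differences will be evaluated using t-tests, Mann-Whitney U test (or other non-parametric tests), chi-square methods", and so on. Neither section says whether the unit is the participant or the facility.

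Clustering returns in the next sentence: "In order to assess factors associated with HIV testing/positivity, we will use hierarchical linear models in order to account for clustering of effects". The grouping meant there is by clinic. On the content of these models: "Separate models will be developed for each outcome of interest and covariates of interest include patient characteristics", plus structural and contextual factors. Study arm is not listed. No section says which analysis decides the primary comparison, or how the blocks enter it.

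**The concern.** Participants at one facility share staff, catchment and testing practice, so their outcomes are correlated. The sample size calculation accepts this; the tests listed for arm differences do not reflect it. Chi-square and Fisher's exact tests normally work on individual counts. Used that way here, they treat 5,000 participants per arm as independent when only five facilities per arm were randomized.

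Three things are at stake:

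- Any interval for the primary effect built on the same basis would be too narrow, whatever the effect size.
- HIV positivity among those tested (yield) is a secondary objective in both aims and has no large assumed effect to protect it.
- A primary effect much smaller than planned could be declared significant when a valid analysis would not support it.

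The plan also leaves open two analyses that can disagree. In an unblinded trial that choice should be fixed before outcome data are seen.

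**Working it through.** **Inputs.** Five facilities per arm, ICC 0.004, type I error 0.05 (sidedness not stated; two-sided assumed). Aim 1: 1,000 per facility; coverage 10% (optimized care) and 60% (self-testing). Aim 2: 600 per arm, so 600/5 = 120 per facility; coverage 20% and 40%. The schema gives 500 per site for Aim 2, so that size is shown too. Equal facility sizes are assumed and blocking is ignored, except where paired figures are given.

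**The plan's own Aim 1 power.** Design effect DE = 1 + (m − 1) × ICC = 1 + 999 × 0.004 = 4.996. Effective sample size = 5,000/4.996 = 1,000.8 per arm. Two-sided power is 98.9% for 5% vs 10% and above 99.9% for 10% vs 60%. This agrees with the stated figure of at least 95%, so the power statement does include clustering.

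**Type I error of a participant-level test with no arm effect** = 2 × [1 − Φ(1.96/√DE)]:

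| Comparison | DE | √DE | Type I error | Simulated |
|---|---|---|---|---|
| Aim 1 coverage, m = 1,000 | 4.996 | 2.24 | 38.1% | 38.4% |
| Aim 2, m = 120 | 1.476 | 1.21 | 10.7% | 10.7% |
| Aim 2, m = 500 | 2.996 | 1.73 | 25.7% | 25.9% |

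The simulation drew 40,000 beta-binomial trials with 5 + 5 facilities. In the same trials a t-test on facility proportions (8 df) rejected in about 5%.

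**Aim 1 yield, self-testing vs optimized care.** The documents give no ICC for positivity, so 0.004 is borrowed. Coverage of 10% and 60% of 1,000 gives 100 and 600 tested per facility, with design effects 1 + 99 × 0.004 = 1.396 and 1 + 599 × 0.004 = 3.396. The ratio of true to assumed variance is (1.396/500 + 3.396/3,000)/(1/500 + 1/3,000) = 1.682, which gives a type I error of 13.1% (simulated 12.7% to 13.0% for assumed positivity of 3% to 10%).

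**Sensitivity to the ICC.** Over an assumed range of 0.001 to 0.04, type I error runs from 16.6% to 75.9% for Aim 1 coverage and from 6.4% to 41.4% for Aim 2 at 120 per facility. For yield, the same formula gives variance ratios of 1.170 and 7.817, hence 7.0% to 48.3%.

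**95% interval half-widths at the assumed effects.**

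- Aim 1: participant-level SE = √[(0.09 + 0.24)/5,000] = 0.00812, × 1.96 = 1.6 points. Cluster-based SE = 0.00812 × 2.235 = 0.01816, × 2.306 (t, 8 df) = 4.2 points.
- Aim 2, m = 120: participant-level SE = √[(0.16 + 0.24)/600] = 0.02582, × 1.96 = 5.1 points. Cluster-based SE = 0.02582 × 1.215 = 0.03137, × 2.306 = 7.2 points.

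**Do the planned primary conclusions change?** Aim 1: 0.50/0.00812 = 62 falls to 0.50/0.01816 = 28. Aim 2 (m = 120): 0.20/0.02582 = 7.7 falls to 0.20/0.03137 = 6.4. Both stay significant.

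**Where the conclusion would flip.** Find the smallest gap d with d/SE(d) = 1.96 (participant-level SE) and with d/SE(d) = 2.306 (cluster-based SE). Above 10% in Aim 1 these are 1.2 and 3.3 points. Above 20% in Aim 2 (m = 120) they are 4.7 and 6.8 points. Observed gaps between the two values are significant only in the participant-level analysis.

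**The case against.** **The wording may already cover this.** The plan speaks of study arm and other factors of interest, which makes arm itself a factor, and the models then assess factors associated with the same outcomes. The covariate list is not exhaustive. Moreover, t-tests and Mann-Whitney tests suit facility proportions better than a binary outcome, and the list ends with a qualifier about appropriateness. These readings are possible, and a facility-level t-test would be valid. But neither reading is stated, and chi-square and Fisher's tests point the other way. The type I error figures are therefore conditional on the participant-level reading; the missing designation is not.

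**The primary result would survive.** This stands. The flip zones lie far below the planned gaps of 50 and 20 points.

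**The plan mentions no confidence intervals, and part of the widening comes from the choice of degrees of freedom.** Both are true. For Aim 2 at 120 per facility, the half-width goes from 5.1 to 6.1 points from the design effect alone (normal reference), to 6.8 with 12 df (a three-arm model on 15 facilities) and to 7.2 with 8 df. About half of the increase is thus the small-sample reference, which is reasonable with ten facilities. Intervals from the hierarchical models would account for clustering, if arm were in them.

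**Aim 2 counts partners, not index clients.** An index client may receive kits for up to three partners, and the calculation ignores that level. This limits the precision of the Aim 2 figures but not the remedy, because a t-test on facility proportions absorbs correlation among partners of one index client.

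**The yield figure borrows an ICC.** This also stands, and for that reason the range is shown.

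**Conclusion.** The concern holds. The only tests tied to differences between arms are listed without a cluster adjustment, the models that handle clustering are given another purpose, and nothing designates the confirmatory analysis in either aim. Run on participants at the plan's own ICC, the listed tests would have a type I error of about 38% (Aim 1 coverage), 11% or 26% (Aim 2, at 120 or 500 per facility) and about 13% (Aim 1 yield, with a borrowed ICC), against a nominal 5%.

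These figures assume two-sided tests and equal facility sizes. The planned primary effects are large enough to stay significant either way. The point should be fixed for the sake of the intervals, the yield comparison and any smaller effect, but it does not overturn the design.

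**What to change.** In sections 2.5.1 and 3.5.1.1, name one primary analysis of self-testing against optimized standard of care:

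- A two-sample t-test on the 5 + 5 facility proportions (8 df), reported as a difference with its cluster-based 95% interval. For yield, use the unequal-variance (Welch) form, because numbers tested per facility will differ by arm. In simulation its type I error was 4.7% to 4.9%, against 5.4% to 5.6% for the pooled form.
- An acceptable alternative is a mixed model with a facility random effect, arm as the tested term, a small-sample degrees-of-freedom correction, and a stated link and effect scale. For partners in Aim 2 it should also reflect grouping within index client.

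State how the section 2.3.1 blocks are handled. One option is the unpaired 8-df test as primary, with a paired t-test on the five within-block differences (4 df) as a sensitivity analysis; its simulated type I error was 4.9% to 5.2%. Adjusting for all four blocking factors with ten facilities is not advisable. Keep participant-level chi-square, Fisher's and t-tests for description, without p-values for arm.

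The cost is wording only, with no new data. Intervals widen as shown. On the stated inputs, power is about 100% for 10% vs 60% with 8 or 4 df. For 20% vs 40% at 120 per facility (noncentrality 0.20/0.03137 = 6.38) it is 99.98% with 8 df and 99.6% with the paired 4 df. The plan's own 89% for Aim 2 is a separate matter and is not used here.

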2.6. COST AND COST-EFFECTIVENESS METHODS

It is expected that group self-testing will be cost-effective compared to standard of care and optimized standard of care for HIV testing. For facilities, fewer HDA staff would be needed to achieve testing coverage, and it is possible that more positives will be identified. The study will estimate differences in overall costs for both standard of care arms and group self-testing. Costs of HIV testing will be estimated as the average cost per individual who completes an HIV test.

Using the average cost per patient tested we will estimate the cost for identifying each HIV-positive individual. We will compare average cost per HIV-positive individual identified among the three study arms with the primary comparison of optimized standard of care compared to group self-testing. To provide information for HIV program budgets, we will also estimate the annual cost of providing HIV testing at a site under the three strategies evaluated, independent of outcomes.

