2. AIM 1: GROUP SELF-TESTING

2.1. OBJECTIVES

2.1.1. Primary Objectives:

- To determine whether group self-testing in waiting areas of outpatient departments (OPD) and sexually transmitted infection (STI) clinics is superior in regard to number tested compared to optimized standard of care (provider-initiated-testing-and-counseling; PITC)
- To determine whether group self-testing in waiting areas of OPD and STI clinics is cost-effective compared to optimized standard of care using PITC

2.1.2. Secondary Objectives:

- To assess the acceptability of self-testing in waiting areas of OPD and STI clinics
- To determine whether group self-testing in waiting areas of OPD and STI clinics is superior in regard to number of HIV+ individuals identified (testing yield)
- To determine whether group self-testing in waiting areas of OPD and STI clinics is superior in regard to linkage rates for those who identify as HIV-positive compared to standard of care and optimized standard of care (PITC)

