2.6.1. Costs to Provider (HIV Diagnostic Assistant)

Costs will be measured from the perspective of the HDA (the "provider" of HIV testing). We will use micro-costing methods to estimate the cost of HIV testing in each study arm.^{25, 26, 27} We

will first create an inventory of all the resources used to achieve the observed study outcomes. Resources to be captured will include:

- HIV self-test kits
- Standard of care HIV testing supplies - Determine and Uni-Gold test kits
- Other services provided (e.g. counseling interactions)
- Fixed costs of patient care (building space, equipment, human resources)

For each study patient, the quantity (number of units) of resources used will be determined. Unit costs of resources, which are not human subjects data, will be obtained from external suppliers and the site's finance and procurement records and multiplied by the resource usage data to provide an average cost per study patient across centers in each study arm. Costs will be reported as means (standard deviations) and medians (IQRs) in U.S. dollars, using the exchange rate prevailing during the follow-up period.

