2.6.2. Cost-Effectiveness

Using the average cost per patient as described above, we will then estimate the cost per outcome achieved in each arm. Two measures of effectiveness will be utilized for the cost-effectiveness analysis: the proportion of individuals tested for HIV and the cost per HIV-positive individual identified. We will calculate the difference in cost divided by the difference in effectiveness between study arms for both measures of effectiveness.

The price of the self-test (if self-testing were to become widely available in Malawi) is currently uncertain. As such, we will conduct a sensitivity analysis where all costs and outcomes remain constant, and the price of self-tests alone is varied. This analysis will then provide a plausible range of the cost-effectiveness of self-testing.

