6. COST AND COST-EFFECTIVENESS METHODS

It is expected that partner self-testing will be cost-effective compared to optimized standard of care. For facilities, fewer HDA visits by patients should save the time of HDA staff. Partner self-testing may also lead to an increase in HIV-positive individuals identified because clients may be more comfortable doing the test in a private place. The study will estimate differences in overall costs for both optimized standard of care and partner self-testing. The average cost per successful outcome (index partner completes an HIV test) will be calculated.

Using the average cost per patient as described above, we will then estimate the cost for each newly identified HIV-positive partner. We will compare average cost per HIV-positive individual identified between study arms. To provide information for HIV program budgets, we will also estimate the annual cost of providing HIV testing under the two main strategies being evaluated (optimized standard of care and self-testing), independent of outcomes.

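### Aim 1 defines no valid incremental cost per additional HIV-positive person found, so its case-finding cost result rests on comparing average ratios

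*Combined protocol and SAP*

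**What the plan says.** The second primary objective of Aim 1 (section 2.1.1) is "To determine whether group self-testing in waiting areas of OPD and STI clinics is cost-effective compared to optimized standard of care using PITC".

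Section 2.6 sets the base unit: "Costs of HIV testing will be estimated as the average cost per individual who completes an HIV test". It carries that unit to case finding: "Using the average cost per patient tested we will estimate the cost for identifying each HIV-positive individual". It then compares arms: "We will compare average cost per HIV-positive individual identified among the three study arms with the primary comparison of optimized standard of care", the other member of the pair being group self-testing.

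Section 2.6.1 includes fixed costs (building space, equipment, staff) in the resource inventory.

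Section 2.6.2 plans an incremental analysis: "We will calculate the difference in cost divided by the difference in effectiveness between study arms for both measures of effectiveness". The two measures are "the proportion of individuals tested for HIV and the cost per HIV-positive individual identified".

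For Aim 2, the opening of its cost section (numbered 6) says "We will compare average cost per HIV-positive individual identified between study arms". Its section 6.2 plans incremental ratios on the proportion of partners tested and on yield, meaning newly identified HIV-positive partners.

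Neither aim states a value at which an extra test or an extra case would count as cost-effective, or says whether the average or the incremental result leads.

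**The concern.** The objective asks about replacing one strategy with another. That calls for the extra cost and the extra cases of self-testing over optimized care. An average ratio instead sets each arm against no testing at all.

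For tests, section 2.6.2 supplies the incremental ratio. For cases found in Aim 1 it does not, because the quantity it names as effectiveness already has cost in its numerator. Dividing a cost difference by a difference in cost per case does not give a cost per additional case. That leaves the side-by-side averages of section 2.6 as the only usable cost result for case finding. Those averages can favour an arm that finds fewer people with HIV, and their order can depend on how much shared overhead is charged to each arm.

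**Working it through.** **Inputs from the documents.** Section 2.5.1 gives 5 facilities of 1,000 clients per arm (5,000), an ICC of 0.004, and coverage of 10% with optimized care and 60% with self-testing. The cost sections give no figure to reproduce. The stated power of at least 95%, which uses the same coverage inputs, does reproduce. The design effect is 1 + 999 × 0.004 = 4.996 and the effective size is 5,000/4.996 = 1,000.8 per arm. Power is then 98.9% for 5% vs 10% (two-sided 0.05; 96.0% with a t reference on 8 df) and about 100% for 10% vs 60%.

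**Assumed inputs.** All unit costs, positivity values and fixed costs below are illustrations.

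**Formulas.** Tests = 5,000 × coverage. Positives E = tests × positivity. Cost C = tests × cost per test + F, where F is fixed cost per arm. Average ratio = C/E. Incremental ratio = (C3 − C2)/(E3 − E2), with 2 = optimized care and 3 = self-testing.

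**Step 1: averages and increments with F = 0.**

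| Case | Arm | Coverage | USD per test | Positivity | Cost, USD | Positives | Average, USD |
|---|---|---|---|---|---|---|---|
| A | Optimized | 10% | 4 | 5% | 2,000 | 25 | 80 |
| A | Self-test | 60% | 5 | 5% | 15,000 | 150 | 100 |
| B | Optimized | 10% | 5 | 5% | 2,500 | 25 | 100 |
| B | Self-test | 60% | 5 | 4% | 15,000 | 120 | 125 |
| C | Optimized | 10% | 5 | 5% | 2,500 | 25 | 100 |
| C | Self-test | 5% | 4 | 5% | 1,000 | 12.5 | 80 |

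- A: the average ranks optimized care first, with 25 positives against 150. Incremental: 13,000/125 = USD 104 per additional positive and 13,000/2,500 = USD 5.20 per additional test.
- B: the average again ranks optimized care first, with 25 against 120. Incremental: 12,500/95 = USD 131.6.
- C: the average ranks self-testing first although it finds half as many positives. The increment is a saving of 1,500/12.5 = USD 120 per positive forgone.

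Range around case A: with self-testing at USD 3 per test, the averages are 80 and 60 and the increment is 7,000/125 = USD 56, so the average favours the arm that finds more. With self-testing at USD 4 and 3% positivity, the averages are 80 and 133 and the increment is 10,000/65 = USD 154.

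**Step 2: the average carries a hidden threshold.** When E3 > E2, C3/E3 < C2/E2 holds exactly when (C3 − C2)/(E3 − E2) < C2/E2. Ranking on averages therefore judges each extra case against the comparator's own average cost, so a costly comparator makes self-testing easier to favour.

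**Step 3: dependence on fixed cost.** Add the same F to both arms and find where the ranking flips.

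- A: 80 + F/25 = 100 + F/150, so F = USD 600 per arm (23% of the optimized arm's cost, 600/2,600).
- B: 100 + F/25 = 125 + F/120, so F ≈ USD 789 per arm.
- C: 100 + F/25 = 80 + F/12.5, so F = USD 500 per arm.

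An equal F cancels from the cost difference, so the incremental figures in A and B stay at USD 104 and USD 131.6 throughout.

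**Step 4: the second measure of section 2.6.2 taken literally.** In case A, 13,000/(100 − 80) = 650. With self-testing at USD 3 per test, 7,000/(60 − 80) = −350. Both are cost over cost, and the sign turns negative when self-testing is cheaper per case. Neither is a cost per additional positive.

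**The case against.** Five objections deserve an answer.

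1. **A reader might infer from section 2.6 that average cost per positive is the designated primary economic metric.** The wording does not support that. The word primary there picks out the arm pair among three arms.
2. **A reader might infer that the cost-effectiveness objective goes unanswered.** It does not. Section 2.6.2 plans incremental ratios, and the one on proportion tested is valid. The gap is confined to case finding in Aim 1. Aim 2 has no such gap, since its section 6.2 uses yield.
3. **A reader might infer that coverage, the trial's main effect, largely cancels from the average in general.** It cancels exactly only if cost is proportional to tests. Section 2.6.1 includes fixed costs: at an assumed USD 5,000 per arm, USD 4 per test and 5% positivity, cost per positive falls from USD 280 at 10% coverage to USD 113 at 60%. The incremental ratio is no better on this score when unit cost and positivity are constant. At USD 5 and 5% it is 12,500/125 = USD 100 for 10% vs 60%, and 5,000/50 = USD 100 for 10% vs 30%. Insensitivity to coverage is therefore not the ground for the change.
4. **The reversals need particular inputs.** This stands. They end at modest fixed costs, and case C needs self-testing to halve coverage when the plan expects a sixfold rise. In case B, the averages and the increment both say that self-testing costs more per case. Without a stated value per case found, the two cannot be said to conflict.
5. **The second measure may be loose wording for the number of positives.** That is plausible, since Aim 2 names yield. The Aim 1 text nevertheless names a cost, and correcting it would still leave unsaid which result supports the conclusion.

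**Conclusion.** The point holds in a limited form. As written, Aim 1 gives no valid incremental cost per additional HIV-positive person found, so the side-by-side averages are its only usable cost figure for case finding. Under the assumed inputs, those averages can rank an arm with 25 positives above one with 150, and the order flips at fixed costs of about USD 500 to 790 per arm. With other assumed inputs the average favours the arm that finds more. The real cost mix and positivity are not in the documents, so the likelihood of a misleading ranking cannot be stated. The missing increment is a matter of the text alone and does not depend on these assumptions. For Aim 2, all that is missing is which result leads.

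**What to change.** In section 2.6.2, replace the second effectiveness measure with the number of HIV-positive individuals identified. In sections 2.6 and 2.6.2, state that the cost-effectiveness of group self-testing against optimized standard of care is judged on two incremental ratios: cost per additional HIV-positive individual identified and cost per additional person tested. Express costs and outcomes both per 1,000 eligible OPD/STI attendees, so that arms with different attendance are compared on one base. Report average cost per test and per positive by arm as descriptive budget figures.

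For Aim 2, add one sentence saying that the incremental ratios in its section 6.2, and not the average comparison at the start of its cost section, are the basis for the conclusion.

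The cost is a wording change. Resource use (section 2.6.1) and attendance, tests and positives (section 2.3.2) are already to be collected. The small downside is a headline figure less familiar to programme managers than average cost per positive, which would still be reported.
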